Intervention: The Coach2Move approach is stepwise implemented in 16 physiotherapy practices. On each site, at least one physiotherapist in geriatrics and one physiotherapist will receive a two-day training in the Coach2Move approach, which makes use of elements of the Hypothesis Oriented Approach for Clinicians (HOAC-II) and the International Classification of Functioning and Health (ICF). Participants receive physiotherapy according to the Coach2Move approach instead of the usual care physiotherapy.

Main study parameters/endpoints: In this study, each participant is measured four times. The first, being the baseline measurement (T0) is prior to physiotherapeutic treatment, while the second is directly after ending the treatment (T1). The following two are respectively six- (T2) and twelve months (T3) after the moment the participant started the treatment.

The primary outcome measures are the cost per quality-adjusted life year (QALY) gained, mobility measured by the modified Timed up and Go (TUG) and the level of moderate physical activity (LAPAQ). Secondary outcomes include: quality of life (EQ-5D), the degree of frailty (Evaluative Frailty Index for Physical activity), perceived effect (Global Perceived Effect and Patient Specific Complaints) and health care utilization costs.

In addition, qualitative data of experiences in implementation of Coach2Move will be gathered from interviews with patients and focus groups with PTG's and PTs.

The quantitative analysis will be based on quality indicators of medical records of patients for each physiotherapist scored by the researcher. The files in the control period are compared with those after implementation of Coach2Move.

Nature and extent of the burden and risks associated with participation, benefit and group relatedness: The physiotherapeutic process according to the Coach2Move strategy does not have more risk compared to usual care physiotherapy. The additional load related to the study participants are being exposed to consists of the three measurement moments in which questionnaires are being conducted. These moments each will take the patients approximately 60 minutes.

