A new and promising approach to help frail older adults to increase their levels of physical activity is Coach2Move. This strategy, based on clinical reasoning conform the Hypothesis Oriented Algorithm for Clinicians (HOAC-II) and the International Classification of Health (ICF), provides guidance in the diagnostic and therapeutic process to physiotherapists [7-9]. This is complemented with behavioural changing techniques such as motivational interviewing and shared decision-making, which are a valuable addition to usual physiotherapy[10]. By effectively using the context of the patient and focusing on strengths and the potential to adapt instead of the disease and the weaknesses, a high level of adherence to physical activity is expected to maintain. In a previous trial (CMO registration number: 2012/233), we demonstrated that the Coach2Move approach is superior to regular physiotherapy in terms of increasing physical activity, reducing frailty, improving quality of life and reducing healthcare costs [11]. In short, in less physiotherapeutic sessions, better outcomes were realized. It is therefore that the RIVM (Rijksinstituut voor Volksgezondheid en Milieu) has appraised the Coach2Move approach as good evidence for effectiveness.

Despite these promising findings, we still have questions regarding the generalisability of these findings. Our reservations towards the generalisability of the approach are caused by the following:

1. We included a modest (n=130), yet somewhat selective study sample: nearly half of the eligible individuals declined randomisation and thereby participation. We need to understand how this group of eligible non volunteers respond to Coach2Move. Therefore, we will use a study design that avoids randomisation at the patient level.
2. The Coach2Move approach significantly increased the level of moderate physical activity among the treatment group and reduced levels of frailty significantly after 6 months, but the clinical importance of these findings is still unclear. Thus, we need a replication of the effects in the light of physical functioning, a larger more variable study population and a longer follow-up.

In addition, the results from the earlier carried out RCT concerning the cost-effectiveness of Coach2Move have to be replicated on a larger scale.

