7. INVESTIGATIONAL PRODUCTS

a. Coach2Move

The intervention consists of geriatric physiotherapy conform the Coach2Move approach. Coach2Move is a personalized coaching strategy for physiotherapists to elicit physical activity in elderly patients who visit their physiotherapist for mobility problems. This approach helps the PT(G) in clinical reasoning by providing an extensive, pre-structured and systematically organised diagnostic protocol based on the HOAC-II and ICF [7-9]. The diagnostic phase requires more time (60 minutes) than the conventional physiotherapy intake (30 minutes), during which not only impairments and disabilities, but wishes, barriers and facilitators both intrinsic as well as in the context considering physical functioning are profoundly examined. Motivational interviewing is used to find and deal with barriers for becoming physically active and shared decision-making in goal setting.

Physiotherapy conform the Coach2Move strategy is patient focused (tailor made) and goal-oriented. The PT(G) coaches the patient and the environment in reaching and maintaining his/her own goals (self-management).

Another key element of Coach2Move is the knowledge of result among patients. By repeating the measurements conducted at baseline on regular basis (every 6 weeks) and give feedback on the outcomes, patients are aware of the consequences a physical active lifestyle has on their health status. A positive change over time is most likely to increase the adherence of staying physically active.

Based on the extensive intake and in consultation with the patient, a stratified intervention is chosen by picking the best fitting option out of the three patient-tailored intervention profiles with a predefined number of intervention sessions. These profiles have been drawn up to guide the progress throughout the treatment.

These three patient-tailored intervention profiles are defined as follows:

1. Intervention Profile 1 (maximum of five sessions).

Population: Physically inactive older adults with minimal not hindering physical constraints to become (more) physically active.

Intervention: Coaching on self-management and the environment to increase physical activities.

2. Intervention Profile 2 (maximum of eleven sessions).

Population: Older adults with minor or acute mobility problems who can train safe at their own, recovery expected within 2 months.

Intervention:

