The CIRS-G in combination with registration of the physiotherapy intervention during each session and registration of health care utilization will be used to explore whether a PT intervention is adjusted because of the presence of comorbidity, if the presence of comorbidity influences the effect of an intervention, and if comorbidity require other interventions than PT.

a.III Other study parameters

From the physiotherapy patient files information on demographics, medical diagnosis, cultural background and living situation (alone or with partner) are extracted. Furthermore, the number of therapeutic sessions, number of adverse events and healthcare consumption are recorded.

Information on the process of implementation of Coach2Move will be collected by usage of various methods.

The reach of the intervention is tested based on the characteristics of patients included in relation to the total group patients treated in the same practice during the study period and related to the population in the region.

Furthermore, interviews in each practice with two patients will be carried out to get insight in patient experiences in pros and con's of the intervention, the experienced effectiveness and advises to improve the intervention. Over practices, we will guarantee a representative sample of participating patients and possibly context. Moreover, group interviews with PT's and PTG's within each practice will inform us about views and experiences of facilitators and barriers in delivering the Coach2Move interventions and views on which elements on the Coach2Move were effective and which were not, and if the education, peer assessment, EPD, and measurement procedures were viewed as helpful or unhelpful in supporting them to realize behavioural change strategies including needs assessment, problem analysis, shared decisions on SMARTI goals, and monitoring feedback.

Moreover, we will interview two patients in each practice after a period of 12 months after baseline to get insight in patient experiences of maintaining (or not) any lifestyle changes in physical activity made as a result of the intervention and their views of which aspects on the program were helpful and which were less.

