Another aspect of the study is to evaluate the fidelity of the PT(G)'s to Coach2Move. This is done by the scoring of quality indication scores of patient files. PT(G)'s are asked to assess patients conform the Coach2Move approach. This asks for an extensive and thorough intake to require optimal clinical reasoning during the therapeutic process.

By scoring the files on integrality of data, it can give insight in the diagnostic therapeutic process before and during the implementation of Coach2Move. Scoring will be independently carried out by two researchers. Of every participating therapist, 10 files will be scored: 5 during the control period and 5 during the implementation period.

b. Randomisation, blinding and treatment allocation

Coach2Move is rolled-out sequentially to 4 groups; each comprising 4 physiotherapy practices. The time points at which the different practices receive Coach2Move are determined at random.

Randomisation will be carried out by a random number generator operated by an external independent researcher. By the end of the trial, all practices will have implemented Coach2Move (Figure 1).

Blinding takes place at patient level. Although patients receive an information letter prior to participation, the exact goal of the study is not specified to make sure the expectations are not biased by placement in control- or intervention group. It is stated that the study focuses

on gaining a better understanding in physiotherapeutic treatment among older adults and therefore monitors health before- and after the treatment.

Since the Coach2Move strategy relies heavily on a more extensive and thorough intake including the usage of several questionnaires which otherwise would not be used with regular physiotherapy, it is therefore complicated to blind both the participants as well as the researchers since this study uses outcomes otherwise not obtained.

c. Study procedures

Participating subjects are tested on four occasions: prior to the intervention, after 3, 6 and 12 months after commencement of the intervention.

Subjects are exposed to several questionnaires on the four moments of testing. One physical test is carried out on each of these four moments.

Procedure of patients in the study:

1. Registration at physiotherapy practice
2. Information on study
3. Informed consent

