4. First assessment at the start of the intervention (t0) in which a number of measures will be performed. Questionnaires: LAPAQ, EQ-5D, EFIP, PSC and CIRS-G. In addition, the modified TUG is carried out. This assessment will take approximately 60 minutes and is carried out by one of the researchers during the control period or by one of the participating PT(G)'s during the intervention period.
5. Physiotherapy treatment. In either the experimental or the control group, the physiotherapist determines the number of physiotherapy consults that are needed. This is common in physiotherapy. During the intervention period, the patient and the PT(G) will choose the best fitting intervention profile together.
6. The second assessment (t1) at three months after the start of the intervention: questionnaires: LAPAQ, EQ-5D, EFIP, PSC, GPE and healthcare utilization. Again, the modified TUG is carried out. This assessment will take approximately 45 minutes.
7. The third assessment (t2) at six months after the start of the intervention. Questionnaires: LAPAQ, EQ-5D, EFIP, PSC, GPE, healthcare utilization and adherence. The modified TUG is performed. This assessment will also take approximately 45 minutes and is carried out by the researcher.
8. The fourth assessment (t3) at twelve months after the start of the intervention. Questionnaires: LAPAQ, EQ-5D, EFIP, PSC, GPE, healthcare utilization and adherence. The modified TUG is carried out once again. This assessment will also take approximately 45 minutes and is carried out by the researcher.

A randomised selection of participants is asked to join in focus group meetings to share experiences on Coach2Move. Participation is voluntarily.

All participants will be debriefed after the study by sending an information brochure concerning the most important outcomes and conclusions of the study. In addition, the participating practices for physiotherapy will be sent the same information in flyer format, which they can hang in a visible spot in their practice. Dutch magazines and newspapers will be approached to publish the research outcomes, as has happened during the previous trial of Coach2Move.

Procedure of enrolled therapists in the study:

1. Start with physiotherapeutic care as usual.
2. Electronic medical record (EPD) will be provided to support clinical reasoning and monitoring the process.

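### The adverse-event count has no stated source, recorder or time window, and no adverse-event or fall item is named at T1 to T3; if it comes from treatment files, capture ends with treatment and depends on contact that differs by condition

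*Combined protocol and SAP*

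**What the plan says.** Section 8.a.III (Other study parameters) holds the only operational statement on adverse events: "Furthermore, the number of therapeutic sessions, number of adverse events and healthcare consumption are recorded". The sentence just before it concerns the treatment record: "From the physiotherapy patient files information on demographics, medical diagnosis, cultural background and living situation (alone or with partner) are extracted". No definition of an adverse event, recorder or period is given.

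Section 8.c lists the content of each follow-up assessment. At T1 it is "questionnaires: LAPAQ, EQ-5D, EFIP, PSC, GPE and healthcare utilization". At T2 and T3 it is "Questionnaires: LAPAQ, EQ-5D, EFIP, PSC, GPE, healthcare utilization and adherence". The modified TUG is added each time. The lists are the same for both conditions, and none names adverse events or falls.

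On risk, the Summary states: "The physiotherapeutic process according to the Coach2Move strategy does not have more risk compared to usual care physiotherapy". Section 10.d adds that adverse-event risk is thought to be very low. Section 9 contains no analysis of adverse events.

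**The concern.** The participants are aged 70 or over, have mobility problems and are encouraged to be more active. Section 7.a names fall risk as a target of Profile 3, so falls and related injuries are the obvious harms to follow.

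As written, an event that led to no care and happened after treatment ended has no listed route into the count. Those later months are when patients are meant to stay active on their own. During treatment, a file-based count would depend on how often, and how systematically, the therapist sees the patient, and the two conditions differ in this by design. A difference between conditions in the reported number could then reflect opportunity to record rather than harm. A similar number in both could hide a real difference.

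**Working it through.** The documents give no adverse-event rate, session count or treatment duration by condition, so there is no planned figure to reproduce. The check has three parts.

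**1. Which sources could feed the count?**

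| Source | Where | Runs to 12 months? | Tied to adverse events? |
|---|---|---|---|
| Physiotherapy file | 8.a.III, preceding sentence | Only while treatment lasts | By position in the text, not by statement |
| Healthcare-utilisation questionnaire | 8.c, T1 to T3 | Yes | No; reaches events that led to care |
| Diaries and 3-month recall | 8.a.I, economic evaluation | Yes | No; planned for costs |
| Named adverse-event or fall item | 8.c | None listed | – |

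If the 3-month recall is asked at T1 (month 3), T2 (month 6) and T3 (month 12), it covers months 0–3, 3–6 and 9–12. That is 9 of 12 months, with months 6–9 left to the diary.

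**2. How much follow-up would a file-only count miss?**

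Unobserved share = (12 − L)/12, where L is the treatment episode in months. L is an assumption. Two months matches the recovery expected for Profile 2. Three months matches T1, which the Summary puts at the end of treatment and 8.c at three months. Longer values are included because 7.c leaves usual-care duration open.

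- L = 2: 10/12 = 83%
- L = 3: 9/12 = 75%
- L = 4: 8/12 = 67%
- L = 6: 6/12 = 50%

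**3. Could recording differ by condition?**

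- *Towards fewer recorded events under Coach2Move:* the profiles set maxima of 5, 11 and 18 sessions (7.a), usual care has no set frequency or duration (7.c), and of the earlier trial section 2 says: "In short, in less physiotherapeutic sessions, better outcomes were realized".
- *Towards more:* the Coach2Move intake takes 60 minutes against 30, and the therapist repeats the baseline measurements every 6 weeks (7.a).

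Suppose true event rates are equal. Let q be the chance of recording an event that occurs during treatment. Then

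apparent count ratio (Coach2Move / usual care) = (L_C2M × q_C2M) / (L_UC × q_UC).

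With equal q and assumed episode lengths:

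- 3 v 3 months: 3/3 = 1.0
- 3 v 4 months: 3/4 = 0.75
- 2 v 3 months: 2/3 = 0.67
- 3 v 6 months: 3/6 = 0.50

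Equal q is itself an assumption. In the 2 v 3 month case, a recording chance 1.5 times higher under Coach2Move would cancel the deficit (0.67 × 1.5 = 1.0), and a larger one would reverse it. The documents do not allow the net direction to be fixed.

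**The case against.** The strongest reply is that the documents never name the file as the source. Healthcare consumption stands in the same sentence and is collected by questionnaire, so the sentence is not confined to the file. Section 8.a also mentions therapist scoring sheets and registration at each session. The utilisation questionnaire, diaries and recall run in both conditions and could catch events that led to care. All of this stands. A reader might infer that the file is the only source, and the text does not support that. But healthcare consumption has a listed instrument and adverse events have none, and nothing connects the cost instruments to the count.

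Second, no comparison of adverse events is planned, and the Summary's risk statement belongs to the burden-and-risk rationale. That stands too. A reader might infer that a planned safety comparison is invalid, but the protocol contains no such comparison.

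Third, unequal recording is a possibility and not a documented fact. The session figures are maxima with no usual-care count beside them, and 8.c has the physiotherapist decide the number of consults in either group. One might also argue that training makes files more complete, citing the fidelity scoring: "By scoring the files on integrality of data, it can give insight in the diagnostic therapeutic process before and during the implementation of Coach2Move". That scoring concerns the diagnostic and therapeutic process rather than the noting of events, and the electronic record is listed at the usual-care stage, before training. It is weak evidence of a difference.

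Fourth, the documents list instruments by name and do not show their items. The 50-item EFIP or the utilisation questionnaire might touch on falls. Only the absence of a named item can be verified.

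**Conclusion.** The concern holds in a limited form. The plan says adverse events are counted but not from what source, by whom or over what period, and no adverse-event or fall item is named at T1 to T3. Under the natural reading that the treatment file supplies the count, about 50% to 83% of the 12 months is unobserved for assumed episodes of 6 to 2 months. Capture during treatment then depends on contact that differs by condition, with size and direction unknown. The ratios of 0.50 to 1.0 illustrate equal true rates under assumed episode lengths; they are not estimates.

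No endpoint, sample size or planned analysis changes. What is affected is any adverse-event count reported by condition, and any later use of such a count to support the statement of no more risk. Because a better method is available at visits that already take place, this is a worthwhile cheap improvement and more than a missing detail to be written down.

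**What to change.** - **8.c, steps 6–8:** add one fixed item at T1, T2 and T3 on falls, fall injuries and other adverse events since the previous assessment, with a short definition. The researcher asks it in the same way in both conditions; sections 4 and 7.b already have researchers collecting the follow-up data. Anchoring recall to the previous assessment covers 0–3, 3–6 and 6–12 months without a gap, and still does so if T1 falls at the end of treatment instead of at three months.
- **8.a.III:** name this item as the source of the adverse-event count, report it by condition per person-time in a descriptive safety table, and keep file-based counts as supplementary.

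**Cost:** a few minutes at each of three existing visits, and one extra table. Recall of minor events over up to 6 months (T2 to T3) is imperfect. It may not be fully equal between conditions, because 8.b concedes that blinding of participants and researchers is difficult. It would still be a less biased basis than an unspecified count.
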